3.1 Brief Description

This is a prospective, multi-center, single-arm, open-label, Phase II clinical study. Each subject will be followed for 12 months after device placement for the protocol endpoints, and then every 6 months thereafter for those subjects who wish to continue study device use up to a maximum of 3 years.

Follow up office visits will occur at weeks 6, 13, 26 and 52 after study device placement, with monthly contact. For those subjects who wish to continue study device use after 12 months (up to 2 additional years for a total maximum of 3 years), long term follow up office visits will occur every 6 months with contact at the end of each 28-day cycle beginning after the 52-week visit. Additional visits will be conducted if necessary for safety issues.

The study will be conducted at approximately 16 centers in the U.S. It is estimated that approximately 250 subjects will be enrolled to have 2240 evaluable cycles at 12 months. It is planned that 225 of the 250 subjects will be within the 18-35 year age range, with a total of 2015 evaluable cycles. The remaining 25 subjects will be within the 36-40 year age range.

The overall schedule of assessments is presented in table 3:

Table 3: Schedule of Assessments

	Screening	LevoCept Placement	Follow up				Monthly Contact	Exit Visit	Long Term Follow up(max 3 yrs. post insertion)	End of each 28-day Cycle Contact	Exit Visit
	Visit 1	Visit 2 Day 1	Visit 3 6 ± 1w	Visit 4 13 ± 2w	Visit 5 26 ± 2w	Visit 6 52 ± 2w	up to 52 ± 1 w	Visit 2 – Visit 6/Week 52	Every 6 Months post 52± 2 w	Post 52 ± 1 w	Post Visit 6/ Week 52- Year 3
Assessments											
Initiation/Subject Characteristics											
Assessment of Eligibility	X	X									
Distribution of information	X										
Informed consent, PHI and Bill of Rights forms	X										
Demographics and baseline characteristics	X										
Medical/surgical, gynecologic and menstrual history	X										
Safety and Effectiveness											
Vital signs and weight	X	X	X	X	X	X		X	X		X
Height	X										
General physical exam	X					X		X			X
Pelvic exam	X	X	X ¹	X ¹	X ¹	X ¹		X ¹	X ¹		X ¹
Cervical cytology	X ⁶										
Cervical infection test (gonorrhea and chlamydia)	X ^{5,7}										
Transvaginal ultrasound (for verifying study device position)		X	X ²	X ²	X ²	X		X ¹	X ²		X ²
Pregnancy test-urine	X	X	X	X	X	X		X ^{4, 9}	X		X ^{4, 9}
Prior and interval concurrent medication	X	X	X	X	X	X	X	X	X		X

CONFIDENTIAL

Adverse events		X	X	X	X	X	X	X	X		X
Other											
IUD placement		X									
IUD placement ease		X									
IUD placement pain		X									
IUD removal ease						X					X
IUD removal pain						X					X
Concomitant contraception		X	X	X	X	X	X	X	X	X	X
Need for contraception	X	X ⁸	X ⁸	X ⁸	X ⁸	X ⁸	X	X ⁸	X ⁸	X ⁸	X ⁸
Patient trained on E-diary	X ³	X	X	X	X						
E-diary reviewed with subject		X ³	X	X	X	X	X				
End of study medication								X			X

Note: Screening and enrollment visit may be combined if the subject requests and all labs and screening exams are documented as normal.

1. Pelvic exam for LevoCept string check.

2. Transvaginal Ultrasound performed at Visit 6 or Exit visit or indicated.

3. First week of e-diary training, prior to LevoCept placement, to be used as training with the subject. This e-diary data is not a part of data collection or analysis. It is intended to ensure the subject understands how to complete the e-diary during the follow up period.

4. Urine pregnancy test will be done 17 days after removal/study exit by the subject at home, with a follow up call by the study coordinator or PI required to document the results. Note: If LevoCept is removed before 52+2 weeks, Visit 6 activities should be completed for Exit Visit.

5. Screening for cervical infections is required unless negative results have been obtained within three months of the screening visit.

6. Current with ASCCP cervical cancer screening guidelines for subjects who will be 21 or older at time of informed consent.

7. Insertion can occur without receipt of test results if there is no clinical evidence of infection.

8. If a subject believes the study device may have been expelled or is no longer in place, the subject should call for an urgent study visit and refrain from having sex or use appropriate non-hormonal contraception until further evaluation is completed.

9. For subjects exiting the study due to IUD expulsion: A urine pregnancy test will be done approximately 6-8 weeks after the exit visit by the subject at home, with a follow up call by the study coordinator or PI required to document results.

3.2 Study Sample Size

No formal sample size calculations were performed for the study. It is estimated that with 225 subjects enrolled with ages 18-35, a 12-month (13 cycles) Pearl Index of 0.6 (1 observed pregnancy), and 2,015 evaluable cycles, we will observe a 95% confidence interval (CI) for the 12-month Pearl Index of (0.1, 3.3).

4 Primary Efficacy and Safety Variables

For all change from baseline variables, baseline is defined as the last non-missing value on or before the day of study device successful placement. Change from baseline to post-baseline will be calculated as the post-baseline value minus the baseline value. If either the baseline or post-baseline value is missing for a particular variable, change from baseline will be missing.

4.1 Efficacy Variable

The primary outcome measure is effectiveness and will be evaluated as absence of pregnancy during study device use.

E-Diary data from the day of study placement to end of study/exit will collect the following information:

- 1) Menstrual and intermenstrual bleeding;
- 2) Vaginal intercourse;
- 3) Pain with intercourse;
- 4) Use of additional contraception;
- 5) Menstrual pain or cramping;
- 6) LevoCept expulsion

When data is still missing for a day after final attempt to have subject complete E-Diary, Vaginal intercourse, Pain with intercourse and Use of additional contraception will be collected for that specific missing day during monthly contact. The CRF collected data is used as a back-up. It is always preferred for the subject to complete the E-Diary data. If it occurs for a particular day that there is both subject data and CRF collected data, the subject data will take precedence and be used.

1. Pearl index

The primary efficacy variable is Pearl index. The Pearl index based on 28-day cycles and defined as the number of pregnancies per 100 woman-years (with one year comprising 13 28-day cycles). It will be calculated as:

$$\text{Pearl index} = \frac{N \times 1300}{L} = \frac{\text{Number of pregnancies} \times 1300}{\text{Number of woman-cycles of pregnancy at risk}}$$

Where n is the number of pregnancies, L is the number of woman-cycles of pregnancy at risk.

Only pregnancies judged to have occurred during study device use, or for which the estimated date of conception was within 7 days after study device removal or calculated date of expulsion are counted.

The number of woman-cycles of pregnancy at risk is the sum of the number of 28-day cycles for each subjects from the date of study device successful placement through the date of study device removal/expulsion or pregnancy, whichever comes earlier, excluding the following (unless the subject became pregnant in the cycle):

- Cycles where back-up contraception or emergency contraception use was reported by the subject;

- Cycles with no intercourse.

The cycle is defined as 28 days with the day of study device successful placement as cycle 1 day 1. The last cycle of pregnancy risk can be a partial cycle and the number of cycles can have one decimal place. The number of cycles (NC) of pregnancy risk for each subject will be calculated as:

$$NC = \frac{\min(\text{Date of removal/expulsion, Date of conception}) - \text{Date of placement}}{28}$$

The NC is zero for subjects who failed in both study device insertion attempts.

2. Pregnancy rate

Pregnancy rate is defined as the success rate for getting pregnant. Time to pregnancy is defined as the number of days from the first day of study device use to the first documented estimated date of conception.

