### **12.8 Lost to Follow-up**

A subject should not be considered “lost to follow-up” until the site has made at least three contact attempts (e.g. phone calls, e-mail or text message) and a certified letter is sent. The date of the certified letter or last attempted contact by the site is the subject’s exit date, whichever is later. The End of Trial and any Adverse Event or Concomitant Medication eCRFs should be submitted within a week of the subject’s lost to follow-up date. The site should continue attempts to contact the subject monthly for an additional 3 months to bring the subject back to remove the LevoCept IUD.

If after a subject is determined to be lost to follow-up and subsequently becomes available again, and the Principal Investigator determines she is a fit study subject, she can re-join the study.

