6.2.9.9 Physical Examination

Physical examination results will be included in data listings only.

7 Interim Analyses

Interim analyses are planned for this study when all subjects have completed one year of treatment. The analyses for the interim CSR is the same as the planned analyses for the final CSR.

8 Changes in the Conduct of the Study or Planned Analysis

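### SAP 4.1 gives two conflicting Pearl Index denominators: the text drops excluded cycles, the per-subject formula does not, and neither ends risk time for a woman with no removal, expulsion or pregnancy

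*SAP*

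**What the plan says.** SAP 4.1 (Efficacy Variable, Pearl index) defines the index as pregnancies times 1300, divided by the woman-cycles at risk. In words, the woman-cycles run from successful placement "through the date of study device removal/expulsion or pregnancy, whichever comes earlier", "excluding the following (unless the subject became pregnant in the cycle"). Two kinds of cycle are listed for exclusion: "Cycles where back-up contraception or emergency contraception use was reported by the subject" and "Cycles with no intercourse". Protocol 20.6 has the same exclusions, and Protocol 12.7 repeats the one for emergency contraception.

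The SAP then allows the last cycle to be partial and continues: "The number of cycles (NC) of pregnancy risk for each subject will be calculated as". The expression that follows takes the minimum of "Date of removal/expulsion, Date of conception", subtracts the placement date and divides by 28. It has no term for an excluded cycle, and no later sentence subtracts any.

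Three other places bear on when risk time ends. SAP section 7 says "Interim analyses are planned for this study when all subjects have completed one year of treatment". SAP Table 2 fixes Year 1 as study days 1-364, Year 2 as 365-728 and Year 3 as 729-1092. Protocol 12.8 sets the exit date of a woman lost to follow-up: "The date of the certified letter or last attempted contact by the site", whichever is later. It also lets her re-join if she becomes available again.

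**The concern.** The Pearl Index is the primary efficacy variable, and its denominator should be computable in only one way. Two programmers working from SAP 4.1 could produce different denominators, and each could point to a sentence that supports the result. Coding the formula as printed puts cycles without the intended exposure to pregnancy risk back into the denominator, which lowers both the index and its upper limit.

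The second gap concerns women who have none of the three stopping events. At the one-year analysis this includes everyone who continues into the extension with the device in place, as well as women lost to follow-up whose device was never removed. For them the formula has no end date. Whoever programs it must supply one, and the SAP does not say which.

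**Working it through.** **Inputs.** From the protocol's Sample Size section: 225 women aged 18-35, an average of 10 cycles each, 1% with no e-diary data, 9.2% of cycles without intercourse or with back-up contraception, 2,015 evaluable cycles, one pregnancy, Pearl Index 0.6. From SAP 4.1: index = pregnancies × 1300 / cycles.

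**1. Reproduce the plan's figures.**
- Cycles: 225 × 0.99 × 10 × (1 − 0.092) = 2,022.6, against 2,015 stated (0.4% apart). The planned figure is therefore net of the exclusions.
- Index: 1 × 1300 / 2,015 = 0.645, which rounds to the stated 0.6.
- Exact Poisson upper limit for one event is 5.572, so 5.572 × 1300 / 2,015 = 3.59. The exact interval is (0.02, 3.59). The stated interval of (0.1, 3.3) does not follow from 2,015 cycles by this method; see the objection.

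**2. Formula against text for one woman.** Take 364 days of use and two excluded cycles. Formula: 364 / 28 = 13.0. Text: 13.0 − 2 = 11.0.

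**3. Formula against text for the trial.** Putting the 9.2% back gives 2,015 / 0.908 = 2,219 cycles.

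| | Text (exclusions applied) | Formula taken literally |
|---|---|---|
| Cycles | 2,015 | 2,219 |
| Pearl Index | 1300 / 2,015 = 0.645 | 1300 / 2,219 = 0.586 |
| Exact 95% upper limit | 3.59 | 5.572 × 1300 / 2,219 = 3.26 |

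The denominator is 10.1% larger (1 / 0.908 = 1.101). The index and upper limit are both 9.2% lower. Starting instead from 225 × 0.99 × 10 = 2,227.5 cycles gives 0.584 and 3.25.

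**4. Women with no stopping event.**
- *Continuing at one year:* no removal, expulsion or conception date exists, so the minimum has no argument and the count is undefined. Table 2 supplies a day-364 boundary, but the formula does not refer to it.
- *Lost to follow-up:* also undefined. If the Protocol 12.8 exit date were inserted, time after her pregnancy status was last known would be counted, because that date records an attempt at contact.
- *Lost, re-joined and later removed:* now defined, but the formula runs from placement to removal and includes the unobserved gap.
- Membership of the Evaluable for Pregnancy population (SAP 5.5) does not limit this, since it asks for only one report of pregnancy status after enrolment.

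The documents give no loss rate, so the size of this second part cannot be computed from them.

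**The case against.** The strongest reply is that the formula is only a gross count. It follows directly after the sentence on partial last cycles, so it can be read as the step that converts elapsed days into cycles, with the exclusions stated a few lines earlier applied afterwards. This has force. A reader might infer that the SAP has decided to count excluded cycles, and the documents do not support that: SAP 4.1 and Protocol 20.6 both state the exclusions, and nothing says the formula overrides them. What remains is that the SAP calls the result cycles of pregnancy risk and never states the subtraction.

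A reader might also infer that every gap biases the index downward. That is not shown. For continuing or lost women the count is undefined; if they dropped out as missing, the denominator would shrink and the index would rise. Over-counting needs a late date to be inserted, and the SAP nowhere says to use the Protocol 12.8 date. SAP 6.1 restricts efficacy analyses to observed data unless otherwise specified, and Listing 16.2.1.1 carries dates of last device exposure and last contact, so better dates are available. The SAP still does not tie any of them to the denominator.

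The planned interval of (0.1, 3.3) may suggest that the sponsor already used undeducted cycles, since a score interval reproduces it at about 2,219 to 2,250 cycles. The all-ages target of 2,240 cycles fits too, so the cause cannot be settled from the documents.

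Finally, both index values round to 0.6, and the documents set no success threshold for this Phase II study. That limits the consequence. However, Table 14.2.1 reports two decimals, so the difference would show.

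**Conclusion.** The concern holds as an unreconciled conflict between formula and text, together with a missing end of risk time. If the formula is coded as printed, the denominator is about 10% too large: 2,219 cycles against 2,015, an index of 0.59 against 0.65, and an exact upper limit of 3.26 against 3.59. These figures rest on the plan's own assumptions of 9.2% excluded cycles and one pregnancy; a different share of excluded cycles would scale the error accordingly.

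For women with no stopping event, the conclusion is that the rule is undefined. Its effect has no known size, and its direction depends on what a programmer inserts. No decision rule in the documents is shown to change, but the primary endpoint should not depend on which of two adjacent statements is coded.

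**What to change.** Replace the per-subject formula in SAP 4.1 with a cycle-level sum:

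- For each 28-day cycle of Table 2, count days at risk in the cycle divided by 28.
- Give zero to the cycles that the text already excludes, unless conception occurred in them. Keep the exclusion criteria as they stand.
- End risk time at the earliest of removal, expulsion, conception, the last date with documented pregnancy status, and the analysis cut (day 364, 728 or 1092, as in Table 2).
- State which records count as documented pregnancy status, and that the contact-attempt date of Protocol 12.8 is not one of them.
- State that an unobserved gap before a woman re-joins is not counted.

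The cost is SAP wording and programming, with no new data collection. Compared with coding the present formula literally, the reported Pearl Index becomes slightly less favourable.

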#### **12.5 Early Discontinuation Visit**

If a subject requests LevoCept removal because of an adverse event, the Study Exit Visit described in Section 12.3 above should be completed and documented on the CRF at the time of LevoCept removal. The subject will be followed until resolution of the event or 30 days after removal, whichever occurs first. Subjects experiencing an ongoing adverse event will continue to receive the appropriate follow-up medical care.

If a subject requests early discontinuation and LevoCept removal to become pregnant, the Study Exit Visit should be completed and documented on the CRF at the time of LevoCept removal. Additionally, subjects shall be followed for either; six (6) months, until they decide to no longer try to conceive or they become pregnant, whichever comes first. Outcome data regarding subject's ability to conceive, or the decision to no longer try to become pregnant will be collected via subject contact and documented.

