14.1.11.3 Both Prior and Concomitant Medication (All Enrolled Subjects)

Update the cell at first column first row to 'Patients with both prior and Concomitant Medications'.

CONFIDENTIAL

Sebela Pharmaceuticals Development LLC
CMDOC-0022

Page x of y

Table 14.2.1
Pearl Index (EP Population)

	Number of Subjects	Number of Pregnancies	Number of Woman-Cycles at Risk	Pearl Index	95% CI for Pearl Index
1-Year					
All EP Subjects	n	n	n	x.xx	x.xx, x.xx
EP Subjects by Parity					
Parous	n	n	n	x.xx	x.xx, x.xx
Nulliparous	n	n	n	x.xx	x.xx, x.xx
EP Subjects by BMI					
Underweight (<18.5)	n	n	n	x.xx	x.xx, x.xx
Normal (18.5-24.9)	n	n	n	x.xx	x.xx, x.xx
Overweight (25.0-29.9)	n	n	n	x.xx	x.xx, x.xx
Obese (>=30)	n	n	n	x.xx	x.xx, x.xx
2-Year					
All EP Subjects	n	n	n	x.xx	x.xx, x.xx
EP Subjects by Parity					
Parous	n	n	n	x.xx	x.xx, x.xx
Nulliparous	n	n	n	x.xx	x.xx, x.xx
EP Subjects by BMI					
Underweight (<18.5)	n	n	n	x.xx	x.xx, x.xx
Normal (18.5-24.9)	n	n	n	x.xx	x.xx, x.xx
Overweight (25.0-29.9)	n	n	n	x.xx	x.xx, x.xx
Obese (>=30)	n	n	n	x.xx	x.xx, x.xx
Cumulative 2-Year					
.....					
3-Year					
.....					
Cumulative					

EP=Evaluable for Pregnancy.

Reference: Listing xxx.

Program Location: \\xx\xxx\xxx\xxx\xxxxxx\xxxxxxxxxxxxxxxxxxxx\xxxx\xxxxx.sas

date

time

Programmer note:

1.Table will continue with for Cumulative 2-Year, 3-Year,Cumulative

CONFIDENTIAL

Sebela Pharmaceuticals Development LLC
CMDOC-0022

Page x of y

Table 14.2.2
Pregnancy Rate (EP Population)

	Parous (N=xx)	Nulliparous (N=xx)	All Subjects (N=xx)
Number of Subjects with Pregnancy	n (%)	n (%)	n (%)
Number of subjects who was not Pregnant(Censored)	n (%)	n (%)	n (%)
Pregnancy Free (Days)			
Pregnancy Rate[1]			
1-Year	xx	xx	xx
2-Year	xx	xx	xx
Cumulative 2-Year	xx	xx	xx
3-Year	xx	xx	xx
Cumulative	xx	xx	xx
Range (Subjectswith Pregnancy)	xx -xx	xx -xx	xx -xx
Range (All Subjects)	xx -xx	xx -xx	xx -xx

[1] Kaplan-Meier product-limit estimates.

Reference: Listing xxx.

Program Location: \\xx\xxx\xxx\xxx\xxxxxx\xxxxxxxxxxxxxxxx\xxxx\xxxxx.sas

date

time

CONFIDENTIAL

Sebela Pharmaceuticals Development LLC
CMDOC-0022

Page x of y

Table 14.3.1.1.1
Overall Summary of Treatment-Emergent Adverse Events (Safety Population)

	Events (N=xx) n	Subjects (N=xx) n (%)
Onset Time Frame:		
Missing	n	n (%)
From Day 1 through Day 42(Week 6)	n	n (%)
From Day 43 through Day 91(Week 13)	n	n (%)
From Day 92 through Day 182(Week 26)	n	n (%)
From Day 183 through Day 364(Week 52)	n	n (%)

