Program Location: \\xx\xxx\xxx\xxx\xxxxxx\xxxxxxxxxxxxxxxx\xxxx\xxxxx.sas

date

time

CONFIDENTIAL

Sebela Pharmaceuticals Development LLC
CMDOC-0022

Page x of y

Listing 16.2.6.4
Pregnancy Notification (All Enrolled Subjects)

								Estimated		
Subject ID	Serum Collection Performed	Collection Date	Test Result	Serum Test Result (mIU/L)	Date of Last Menstrual Period Before Pregnancy	Method [1]	Date Gestational Age Determined	Gestational Age (weeks)		
									Date of Conception	Date of Delivery
xxx-xxx	No, Explain									
xxx-xxx	Yes	YYYY-MM-DD	Negative	xx	YYYY-MM-DD		YYYY-MM-DD	YYYY-MM-DD	YYYY-MM-DD	2
xxx-xxx	Yes	YYYY-MM-DD	Positive	xx	YYYY-MM-DD	Abdominal/Pelvic Exam, Ultrasound	YYYY-MM-DD	YYYY-MM-DD	YYYY-MM-DD	3
xxx-xxx	Yes	YYYY-MM-DD	Positive	xx	YYYY-MM-DD	Investigator Estimation, Specify	YYYY-MM-DD	YYYY-MM-DD	YYYY-MM-DD	8

[1] Method used to determine gestational age.

Program Location: \\xx\xxx\xxx\xxx\xxxxxx\xxxxxxxxxxxxxxxx\xxxx\xxxxx.sas date time

CONFIDENTIAL

Sebela Pharmaceuticals Development LLC
CDOC-0022

Page x of y

Listing 16.2.6.5 Pregnancy Outcome (All Enrolled Subjects)

Subject ID	Date of Birth or Termination	Fetal Status	Gestational Age (weeks)	Weight (lbs) / Weight (ozs) / Height (inches)	Sex/ Apgar Score (1 minute)/ Apgar Score (5 minutes)	Maternal Complications	Prenatal Events	Postnatal Events	Multiple Birth	Second Baby	
										Weight (lbs) / Weight (ozs) / Height (inches)	Sex/ Apgar Score (1 minute)/ Apgar Score (5 minutes)
xxx-xxx	YYYY-MM-DD	PreTerm Birth	xx	xx/ xx/ xx	xx/ xx/ xx	xxxxx	xxxxx	xxxxx	No		
xxx-xxx	YYYY-MM-DD	Full Term Birth	xx	xx/ xx/ xx	xx/ xx/ xx	xxxxx	xxxxx	xxxxx	Yes	xx/ xx/ xx	xx/ xx/ xx
xxx-xxx	YYYY-MM-DD	Spontaneous Termination	xx	xx/ xx/ xx	xx/ xx/ xx	xxxxx	xxxxx	xxxxx	Yes	xx/ xx/ xx	xx/ xx/ xx
xxx-xxx	YYYY-MM-DD	Unknown	xx	xx/ xx/ xx	xx/ xx/ xx	xxxxx	xxxxx	xxxxx	Yes	xx/ xx/ xx	xx/ xx/ xx

Program Location: \\xx\xxx\xxx\xxx\xxxxxx\xxxxxxxxxxxxxxxx\xxx\xxxxx.sas

date

time

CONFIDENTIAL

Sebela Pharmaceuticals Development LLC
CMDOC-0022

Page x of y

Listing 16.2.6.6
Return to Fertility (All Enrolled Subjects)

Subject ID	Subject Desire Pregnancy	If Yes, Mark Outcome	Date of Conception (If Pregnancy Occurred)
xxx-xxx	No		
xxx-xxx	Yes	Pregnancy Occurred	YYYY-MM-DD
xxx-xxx	Yes	Pregnancy Did Not Occur	
xxx-xxx	Yes	Lost To Follow-up	

Program Location: \\xx\xxx\xxx\xxx\xxxxxx\xxxxxxxxxxxxxxxx\xxxx\xxxxx.sas date time

CONFIDENTIAL

Sebela Pharmaceuticals Development LLC
CMDOC-0022

Page x of y

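### The SAP's time-to-pregnancy definition for the Kaplan-Meier rate omits the Pearl Index event window and, in the supplied text, a censoring date, so read literally it could count conceptions after removal or expulsion

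*SAP*

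**What the plan says.** SAP 4.1 opens with the general outcome: "The primary outcome measure is effectiveness and will be evaluated as absence of pregnancy during study device use". Two measures follow.

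- **Item 1, Pearl Index.** The numerator is restricted: "Only pregnancies judged to have occurred during study device use", or those for which the "estimated date of conception was within 7 days after study device removal or calculated date of expulsion are counted". Exposure stops at removal, expulsion or pregnancy, whichever is earliest.
- **Item 2, pregnancy rate.** "Pregnancy rate is defined as the success rate for getting pregnant". Time to pregnancy is "the number of days from the first day of study device use to the first documented estimated date of conception". The item mentions neither removal, expulsion, the 7-day window nor censoring.

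SAP Table 14.2.2 reports the rate as Kaplan-Meier product-limit estimates in the Evaluable for Pregnancy (EP) population. It labels the non-pregnant women as censored but does not say when. SAP 6.1 says how time-to-event variables are summarised and gives no censoring rule. The supplied text passes from 6.2.6 to 6.2.9.

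The protocol collects pregnancy information after the device is gone:

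- a home test 17 days after removal (12.3.1 and the later exit-visit section);
- a home test about 6 to 8 weeks after the exit visit following an expulsion (12.3.2);
- for women who stop in order to conceive, "subjects shall be followed for either; six (6) months, until they decide to no longer try to conceive or they become pregnant" (12.5), with any conception date shown in SAP Listing 16.2.6.6.

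**The concern.** Protocol 5.1 measures failure by both the Pearl Index and the life table, so the two should count the same pregnancies. As written, only the Pearl Index has an event window. A conception three weeks after an expulsion, or two months after a removal requested in order to conceive, is outside the Pearl numerator. It still has a documented estimated conception date, so a program that follows item 2 word for word would treat it as an event.

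The planning assumption is a single pregnancy in year 1. At that count, one misclassified conception is enough to double the rate, and Tables 14.2.1 and 14.2.2 could then disagree on the same data. Years 2 and 3 may be more exposed: the entry criterion on avoiding pregnancy covers only 12 months, and fewer women remain at risk.

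A smaller effect needs no extra conception. Censoring at removal, at the 17-day test, at the post-expulsion test or at the end of fertility follow-up gives different risk sets, and the supplied text does not choose among them.

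**Working it through.** **1. The plan's own figure.** SAP 3.2 assumes 1 pregnancy in 2,015 evaluable cycles. Pearl Index = pregnancies × 1300 / cycles = 1 × 1300 / 2,015 = 0.645, which agrees with the stated 0.6. The documents state no Kaplan-Meier figure to reproduce. The confidence interval printed with the Pearl Index is not used here.

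**2. The two rules side by side.**

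| | Pearl Index (SAP 4.1, item 1) | Kaplan-Meier (SAP 4.1, item 2) |
|---|---|---|
| Event | conception on device or within 7 days after removal/expulsion | first documented estimated conception |
| End of observation | removal, expulsion or pregnancy | not stated in the supplied text |

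**3. Can a later conception reach the table?** Under SAP 5.5 a woman aged 18 to 35 enters EP with one report of pregnancy status, no pre-treatment pregnancy and one cycle with intercourse and no backup or emergency contraception. Conceiving after removal does not take her out. Her conception date is collected, and item 2 does not exclude it.

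**4. Size, as an illustration.** The inputs are:

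- Women: 225 × 0.99 = 222.75, taken as 223 (225 aged 18 to 35, with 1% giving no e-diary data, from the protocol's Sample Size section).
- Time on device: an average of 10 cycles (same section), read here as mean use within the first 13 cycles with exponential discontinuation (assumption). Solving (1 − e^(−13λ))/λ = 10 gives λ = 0.0423 per cycle and 12-month continuation e^(−13λ) = 0.577.
- One on-device pregnancy at day 182 (assumption).
- k conceptions, each 14 to 114 days after removal and all within year 1 (assumption; the documents give no k). Women who did not conceive are censored at removal under both rules.

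By hand for k = 0: day 182 is 6.5 cycles, so about 223 × e^(−0.0423 × 6.5) = 223 × 0.760 ≈ 169 women are at risk, and the rate is 1/169 = 0.59%. An extra event against a risk set of similar size adds about the same again.

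Averages over 1,000 simulated data sets, with the crude proportion (1 + k)/223 as a check that does not depend on drop-out:

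| k | Censored at removal | Item 2 read literally | (1 + k)/223 |
|---|---|---|---|
| 0 | 0.59% | 0.59% | 0.45% |
| 1 | 0.59% | 1.19% | 0.90% |
| 2 | 0.59% | 1.76% | 1.35% |
| 3 | 0.59% | 2.34% | 1.79% |
| 5 | 0.59% | 3.48% | 2.69% |

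From 0 to 5 the literal rate rises by (3.48 − 0.59)/5 = 0.58 points per conception. At the same cycle count the Pearl Index stays at 0.645 for every k, because its own rule leaves these conceptions out. The doubling at k = 1 appears in both the simulated and the crude columns, so it does not depend on the drop-out assumption.

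**The case against.** A reader might infer that the plan counts wanted pregnancies after removal as contraceptive failures. The documents do not say that. SAP 4.1 sets the outcome as pregnancy during device use before either measure is defined. Protocol 5.1 uses the same limit, and Protocol 20.6, which also contains the Kaplan-Meier analysis, includes pregnancies judged to have occurred with a device in place. Return-to-fertility outcomes have their own listing, and nothing routes Listing 16.2.6.6 into Table 14.2.2. Nor does any section make the post-removal or post-expulsion follow-up periods Kaplan-Meier risk time; they are follow-up procedures. A censoring rule may also sit in SAP 6.2.7 or 6.2.8, so its absence cannot be asserted for the whole SAP.

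The size is open to challenge too. Women enter seeking to avoid pregnancy for 12 months, and alternative contraception is required for two weeks after any removal, so zero intended conceptions in year 1 is plausible. The SAP names the Pearl Index as the primary efficacy variable, and Protocol 20.6 describes the life table as further assessment.

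All of this stands against the stronger reading. It does not settle the operative rule. Protocol 20.6 says device in place, while the protocol's Statistical Methods summary and the Pearl item extend to 7 days after removal or expulsion. The same summary also counts all pregnancies in an intent-to-treat analysis. None of these statements gives a censoring date, and the one sentence that defines the Kaplan-Meier time variable carries no limit.

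**Conclusion.** The point holds as a gap in specification. Item 2 is not aligned with the Pearl Index rule or with the outcome it is meant to measure, and its literal application would bias the Kaplan-Meier rate upward. It cannot be said that the two efficacy tables will disagree, only that they could.

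For one true failure the illustrative 1-year rate runs from 0.6% with no later conception to 3.5% with five. The range rests on an assumed number and timing of conceptions, an assumed discontinuation pattern and one assumed pregnancy date; the documents supply none of these. The Pearl Index is unaffected. The conclusion about censoring is limited to the supplied text and would change if SAP 6.2.7 or 6.2.8 states the rule. Even then, item 2 would need a cross-reference to it. The correction is worth making before the analysis because so few events are expected.

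**What to change.** Amend SAP 4.1, item 2, as follows:

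- Kaplan-Meier events are the pregnancies that meet the Pearl Index numerator rule.
- All other women are censored at the earliest of removal or expulsion plus the same 7-day window, last documented pregnancy status, and the analysis cut. Carrying the 7 days into the censoring rule keeps a qualifying conception shortly after removal inside the observed time.
- The success-rate wording is replaced by 1 minus the Kaplan-Meier estimate at the end of each year (days 364, 728 and 1092 in SAP 1.2, Table 2).
- Conceptions outside the window are reported only in the pregnancy and return-to-fertility listings.

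A footnote to Table 14.2.2 can repeat the event and censoring rules. If 6.2.7 or 6.2.8 already contains them, a cross-reference from item 2 is enough. The cost is a few lines of SAP text and one additional derived date, the last documented pregnancy status, which the Pearl Index formula does not use. No new data collection is needed.
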